7.2 Secondary Endpoints

Secondary Safety Endpoints:

- Occurrence of SAEs, MAAEs, and PIMMCs in 12 treatment groups through 12 months after the last dose of study vaccine
- Occurrence of any AEs leading to study withdrawal
- Frequency and severity of unsolicited AEs for 21 days following each vaccination
- Occurrence of clinical safety laboratory abnormalities at all collected time points
- Occurrence of vital sign abnormalities at all collected time points

Secondary Immunogenicity Endpoints:

- Serum HAI and MN antibody responses at all collected time points
- SPR of serum HAI antibody at collected time points

Protocol: BP-I-16-005 Version 2.0

• Seroconversion rate (defined as proportion of subjects achieving either a prevaccination antibody titer of <1:10 and a postvaccination titer of at least 1:40 or a prevaccination antibody titer of at least 1:10 and a 4-fold or greater increase of postvaccination antibody titer; if antibody titer is undetectable, it will be assigned a value of half the lower limit of detection) at all collected postvaccination time points

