7.7.4 Analysis of Secondary Endpoint

7.7.4.1 Analysis of Secondary Safety Endpoint

Serious adverse events, MAAEs, PIMMCs, and AEs leading to study withdrawal will be summarized by study group and system organ class (SOC)/preferred term (PT).

Unsolicited AEs (including clinically significant laboratory and vital sign abnormalities) for 21 days following each vaccination will be summarized by study group, SOC/PT, and further summarized by severity and relatedness.

Clinical safety laboratory abnormalities will be summarized at prevaccination and 7 days after each vaccination by study group.

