3.2.2 Secondary Endpoints

3.2.2.1 Secondary Safety Endpoints

- Occurrence of SAEs, MAAEs, and PIMMCs in 12 treatment groups through 12 months after the last dose of study vaccine
- Occurrence of any AEs leading to study withdrawal
- Frequency, relatedness, and severity of unsolicited AEs for 21 days following each vaccination
- Occurrence of clinical safety laboratory abnormalities at all collected time points
- Occurrence of vital sign abnormalities at all collected time points

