9.1 Adverse Events

An AE is defined as any untoward medical occurrence in a subject enrolled into this study regardless of its causal relationship to IP.

An SAE is defined as any event that results in death, is immediately life threatening, requires inpatient hospitalization or prolongation of existing hospitalization, results in persistent or significant disability/incapacity, or is a congenital anomaly/birth defect. Important medical events that may not result in death, be life threatening, or require hospitalization may be considered SAEs when, based upon appropriate medical judgment, they may jeopardize the

subject or may require medical or surgical intervention to prevent one of the outcomes listed in this definition.

Medically attended AEs are defined as AEs with medically attended visits, including hospital, emergency room, urgent care clinic, or other visits to or from medical personnel (medical doctor, physician assistant, nurse practitioner) for any reason.

Potentially immune-mediated medical conditions are considered adverse events of special interest. The PIMMCs of concern for this study are detailed in Appendix 2, Section 14.2.

AEs are categorized into 'Solicited Local AEs', 'Solicited Systemic AEs', and 'Unsolicited AEs' for AE type. Solicited Local AEs will include local reactions at the injection site with an onset within the 8 days after each vaccination, such as erythema/redness, induration/swelling, and pain. Solicited Systemic AEs will include systemic reactions with an onset within the 8 days after each vaccination, such as fever, myalgia, arthralgia, fatigue, headache, nausea, vomiting, diarrhea, and chills. All solicited local and systemic reactions will be considered as related to IP by the investigator. All other AEs which are not solicited are considered unsolicited.

Days of onset for unsolicited AEs are categorized into '1-8 Days' and '>8 Days' from each IP administration.

Adverse events will be coded using the Medical Dictionary for Regulatory Activities (MedDRA)[®], which provides the primary system organ class (SOC) and preferred term (PT) information.

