All AEs reported after the first dose of IP will be summarized in tables. AEs within 21 days of each dose of IP, and before the date and time of the next dose of IP (if applicable) will be summarized in tables based on each dose only (Dose 1, 2 for Groups A-D, G-J; Dose 1, 2, 3 for Group E, F, K and L). When the time of an AE is missing and the AE start date is on the date of vaccination, then that AE will be considered as happening after the corresponding dose of IP.

All AEs will be summarized by presenting the number and percentage of subjects having any AEs and having each individual adverse event based on SOC and PT, and PT only. At each level of subject summarization, a subject is counted once if the subject reported one or more events. Percentages will be calculated out of the number of subjects as treated per study group in the Safety Set. For the dose-specific AE summaries, percentages will be calculated out of the number of subjects as treated per study group corresponding to Dose 1, Dose 2 or Dose 3.

Unless otherwise stated, AEs will be sorted in descending order by frequency of SOC and PT.

The following summaries, based on Dose 1 only, Dose 2 only, and both Dose 1 and Dose 2 for Groups A-D, G-J and Dose 1 only, Dose 2 only, Dose 3 only, and all Dose 1, Dose 2 and Dose 3 for Groups E, F, K and L will be provided:

- Overview summary of the number and percentage of subjects with any AE, SAE, AE related to IP, AE leading to study withdrawal, AE leading to death, solicited local AE, severe solicited local AE, solicited systemic AE, severe solicited systemic AE, MAAE, PIMMC, unsolicited AE, severe unsolicited AE, and unsolicited AE related to IP
- All AEs by SOC and PT
- All AEs by AE Type and PT
- All AEs by SOC, PT and Severity

- All AEs by SOC, PT and Relationship
- All unsolicited AEs by SOC, PT and Day of Onset

The following summaries with 95% exact CIs using Clopper Pearson method, based on events recorded during the 8 days post each vaccination will be provided as the analysis of primary safety endpoint:

- Solicited Local AEs by Severity
- Solicited Systemic AEs by Severity

All MAAEs and PIMMCs after the first dose of IP will be summarized in a table by SOC, PT and Severity.

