In all by-severity summaries, the severity that will be presented represents the greatest severity captured in the eCRF if a subject reported multiple occurrences of the same AE. The possible severities include "Mild", "Moderate" and "Severe". The missing severity will be imputed as "Severe".

In all by-relationship summaries, the relationship that will be presented represents the greatest relatedness captured in the eCRF if a subject reported multiple occurrences of the same AE. The possible relationship includes "Related" and "Unrelated". The missing relationship will be imputed as "Related".

All AEs will be included in a data listing containing all subject-level data collected in the eCRF. All SAEs, all AEs leading to study withdrawal, MAAEs, PIMMCs and severe AEs will be listed separately.

A listing of SAEs and MAAEs, including a subset of specific PIMMCs for 12 months after the last dose of study vaccine will be presented in the addendum to the CSR once the study is complete.

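### SAP 9.1 omits the unsolicited-only SOC/PT tables by severity and by relationship that Protocol 7.7.4.1 specifies, and SAP 13 does not declare the departure

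*SAP*

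**What the plan says.** SAP 3.2.2.1 lists as a secondary safety endpoint: "Frequency, relatedness, and severity of unsolicited AEs for 21 days following each vaccination". Protocol 7.2 has the same endpoint without relatedness: "Frequency and severity of unsolicited AEs for 21 days following each vaccination". Neither mentions SOC or PT.

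That level of detail comes from the protocol's analysis text. Protocol 7.7.4.1 takes unsolicited AEs as its subject, counting among them laboratory and vital-sign findings of clinical significance, and says that these events "for 21 days following each vaccination will be summarized by study group, SOC/PT, and further summarized by severity and relatedness".

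SAP 9.1 states that "AEs are categorized into 'Solicited Local AEs', 'Solicited Systemic AEs', and 'Unsolicited AEs' for AE type". Its list of outputs then includes "All AEs by SOC, PT and Severity" and "All AEs by SOC, PT and Relationship". One SOC/PT table is limited to unsolicited events, and it is split by day of onset.

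For the by-severity tables, "the severity that will be presented represents the greatest severity captured in the eCRF if a subject reported multiple occurrences of the same AE". A parallel rule keeps the greatest relatedness. SAP 9.1 also says that all solicited reactions will be considered related to the investigational product.

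SAP 13, which records departures from the protocol, names only two exploratory immunogenicity objectives.

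**The concern.** Where SAP 9.1 means unsolicited events only, it says so, as in the day-of-onset table. The severity and relationship tables carry no such limit, so on the plan's own definition of AE type they pool solicited and unsolicited events. Followed literally, the SAP would not deliver the breakdown in Protocol 7.7.4.1, and no reason is recorded.

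What is at stake is how readable the unsolicited safety profile is. Solicited reactions are prompted by diary card and counted as related by rule. Wherever they share a row with unsolicited events, the row no longer shows how severe the unsolicited events were or whether the investigator thought them related. The relationship table is the more exposed of the two: any subject with a solicited reaction is related in the any-AE row, whatever was judged about that subject's unsolicited events.

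**Working it through.** No power, error rate or sample size figure is involved, so the check compares the required analysis with the planned outputs.

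**Step 1. Required.** Protocol 7.7.4.1: unsolicited AEs, by SOC/PT, by severity and by relatedness. The amendment log for protocol version 2.0 lists no change to this section, so the SAP's reference to version 1.2 does not explain the difference.

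**Step 2. Planned AE tables in SAP 9.1.**

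| Output | Unsolicited shown separately | SOC/PT | Severity | Relationship |
|---|---|---|---|---|
| Overview | Yes | No | Severe only | Related only |
| All AEs by SOC and PT | No | Yes | No | No |
| All AEs by AE type and PT | Yes | PT only | No | No |
| All AEs by SOC, PT and severity | No | Yes | Yes | No |
| All AEs by SOC, PT and relationship | No | Yes | No | Yes |
| Unsolicited AEs by day of onset | Yes | Yes | No | No |
| MAAEs and PIMMCs by severity | No (these events only) | Yes | Yes | No |
| Solicited local and systemic AEs by severity | Solicited only | No | Yes | No |

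Tables with unsolicited events separate, SOC/PT and severity: 0. With unsolicited events separate, SOC/PT and relationship: 0.

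**Step 3. Rows affected.** Protocol 6.2.5.2 lists 3 local and 9 systemic solicited reactions, 3 + 9 = 12 terms. Mixing can occur in the rows for PTs shared with these terms, in the SOC rows above them and in the any-AE row. A PT that is not a solicited term holds only unsolicited events, so its row already gives their severity and relationship.

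**Step 4. How a shared PT mixes.** SAP 9.1 defines solicited events by onset within the 8-day period; everything else is unsolicited. Take a hypothetical subject with a mild headache on Day 2 and a severe headache, judged unrelated, on Day 15 after the same dose. The first is solicited and related by rule. The second is unsolicited. Both fall within 21 days of the dose. If they count as one AE, the subject appears once as severe and once as related, and the unrelated judgment on the unsolicited event disappears. With the grades reversed, the unsolicited grade disappears. In the table over all doses, the two events need not follow the same dose.

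**Step 5. What the overview recovers.** It counts subjects with any, severe and related unsolicited AEs, per dose and over all doses. At the total level:

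- not severe = any unsolicited − severe unsolicited
- only unrelated = any unsolicited − related unsolicited

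So relatedness is recoverable as a total, and severity is recoverable except for the split between mild and moderate. None of it is available by SOC or by shared PT.

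**The case against.** The strongest reply is that the endpoint is reported in part and the gap is narrow. The endpoint wording in Protocol 7.2 and SAP 3.2.2.1 does not ask for SOC/PT. The overview gives the main unsolicited totals, and the table by AE type and PT gives unsolicited frequency by term. Most PTs are not solicited terms and are unaffected. Severe AEs, SAEs, MAAEs, PIMMCs and AEs leading to withdrawal have separate listings, and all AEs are listed by subject. The study is descriptive, and the missing tables could be made later from the same data.

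All of this stands, and it limits the point. A reader might infer that the secondary endpoint is not produced at all, or that the severity and causality of unsolicited events cannot be read from any planned table. The documents support neither reading, for the reasons just given.

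It is also fair to say that the SAP does not state whether a solicited and an unsolicited event with one PT are the same AE for the greatest-severity rule. Merging is an inference, though a natural one: SAP 9.1 counts a subject once at each level of summarization, and these tables have no AE-type dimension. Without merging, the row would still pool the two types.

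What the reply does not answer is Protocol 7.7.4.1. It specifies SOC/PT with severity and relatedness for unsolicited events. Subject listings for about 720 subjects in 12 groups are not that summary.

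**Conclusion.** The point holds as a mismatch between the SAP's table list and the protocol's stated analysis. Two specified breakdowns of unsolicited AEs by SOC/PT, one by severity and one by relationship, are absent from SAP 9.1, and SAP 13 does not declare the departure. The loss is confined to the any-AE rows, the SOC rows and the rows for PTs shared with up to 12 solicited terms. The overview partly makes up for it at the total level.

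The documents give no rates for solicited reactions or for their overlap with unsolicited events, so the share of subjects affected cannot be sized, and the conclusion does not need it. It rests on reading all AEs as including solicited reactions, which the SAP's own AE-type definition supports.

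No data are lost and no primary endpoint is touched. The change is worth making because a prespecified secondary safety analysis otherwise lacks its tables.

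**What to change.** In SAP 9.1, add two outputs: *Unsolicited AEs by SOC, PT and Severity* and *Unsolicited AEs by SOC, PT and Relationship*, each per dose within 21 days and over all doses. Keep the two all-AE tables. Solicited reactions already have their own by-severity tables, so nothing else needs to move. If the sponsor prefers not to add the tables, SAP 13 should record the departure from Protocol 7.7.4.1 and the reason.

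In the same edit, reconcile Protocol 6.2.5.2, where the investigator assesses whether solicited reactions are related, with SAP 9.1, which treats all of them as related.

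The cost is two lines of SAP text and an AE-type filter on two existing table programs. No new data collection is needed.

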9.2 Vaccination Site Examinations

The vaccination site examinations include pain, erythema/redness, induration/swelling, and other local symptoms at the site of injection and will be conducted 30 minutes and 8 days post each vaccination, ET if clinically indicated, and unscheduled visits (if the unscheduled visit occurs within 8 days post each vaccinations). The size of measurable erythema/redness and induration/swelling will be categorized as: <2.5 cm, 2.5 - 5 cm, 5.1 - 10 cm, and >10 cm. Vaccination site examination results will be classified according to the FDA Toxicity Grading Scale (See Appendix 3, Section 14.3, Grade 1 = Mild, Grade 2 = Moderate, Grade 3 = Severe, Grade 4 = Potentially Life Threatening) based on quantifiable criteria. The number and percentage of subjects who have vaccination site reactions involving pain, erythema/redness, induration/swelling, and other local symptoms will be summarized separately for each vaccination site reactions involving measurable redness and swelling will be summarized by size category. This summary will be performed on the Safety Set by treatment received according to first, second or third dose as appropriate.

All vaccination site examination results will be included in a data listing containing all subjectlevel data collected in the eCRF. All subjects with severe reaction based on injection site examination will be included in a data listing.

9.3 Clinical Laboratory Evaluations

Laboratory assessments will be performed by a central laboratory. All summaries will be based on the units provided by the central laboratory, no conversion will be done. Clinical safety laboratory evaluations will include the following: hematology, coagulation and chemistry/metabolic panel. Clinical chemistry and hematology laboratory test results will be classified according to the FDA Toxicity Grading Scale (See Appendix 3, Section 14.3, Grade 1 = Mild, Grade 2 = Moderate, Grade 3 = Severe, Grade 4 = Potentially Life Threatening) based on quantifiable criteria; lab results that are normal will be classified as Grade 0. This categorical data will be summarized in shift tables comparing by visit and by maximum postbaseline value with those at the baseline visit. Results will also be classified by the central laboratory as "Low", "Normal", or "High" based on normal reference ranges.

Summary tables presenting observed values and changes from baseline will be displayed for clinical laboratory tests with numeric values by study group for subjects in the Safety Set.

All laboratory results will be included in a data listing containing all subject-level data collected. Any laboratory finding that qualifies as AEs and nonqualifying laboratory abnormalities outside the laboratory's reference range will be toxicity graded according to the FDA Toxicity Grading Scale (Appendix 3, Section 14.3, Grade 1 = Mild, Grade 2 = Moderate, Grade 3 = Severe, Grade 4 = Potentially Life Threatening). Subjects with any clinically significant lab abnormality will also be listed.

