12.1 Appendix 1: Schedule of Events

H5 Influenza Vaccine With Either AS03 or MF59

Protocol: BP-I-16-005 Version 2.0

26 February 2018

Table 12–1Schedule of Events, Groups A to D, G to J

Study visit	Screening	V1	V2 ^a	V3	V4	V5 ^a	V6	V7	V8	V9 ^a (EOS)	ET	Unsch
Study day	-14 to -3	1	4	8	22	25	29	43	142	387	N/A	N/A
Window allowance (days)			V1+3 (±1)	V1+7 (±1)	V1+21 (+3)	V4+3 (±1)	V4+7 (±1)	V4+21 (±3)	V1+141 (±7)	V1+386 (±7)	N/A	N/A
Obtain informed consent	Xb											
Vital sign measurements ^c	Х	Х		Х	Х		Х	Х			Х	X ^d
Height and weight	Х	Xe										
Medical history	Х	Xe										
Perform subject interview ^f			Х	Х	Х	Х	Х	Х	Х	Х	Х	Х
Review diary card ^g			Х	Х	Х	Х	Х	Х			X ^h	X ^h
Distribute diary card ^g and review instructions		X DCI		X DCII	X DCIII		X DCIV					
Distribute measuring tool and thermometer and review instructions		Х			Х							
Collect diary card ^g				X DCI	X DCII		X DCIII	X DCIV				
Concomitant medications	X ⁱ	X ^{e,i}	Х	Xj	Xe	Х	Xj	Х	Х	Х	Х	Х
Concomitant vaccinations	X ⁱ	X ^{e,i}	Х	Xj	Xe	Х	Xj	Х	Х	Х	Х	Х
Complete physical examination ^k	Х											
Targeted physical examination ¹		Xe		Х	Xe		Х				Xď	X ^d
Urine pregnancy test (WOCBP)	Х	X ^{e,m}			X ^{e,m}							X ^d
Review inclusion and exclusion criteria	Х	X ^e			X ^e							

Protocol: BP-I-16-005 Version 2.0

H5 Influenza Vaccine With Either AS03 or MF59

26 February 2018

Study visit	Screening	V1	V2 ^a	V3	V4	V5 ^a	V6	V 7	V8	V9 ^a (EOS)	ЕТ	Unsch
Study day	-14 to -3	1	4	8	22	25	29	43	142	387	N/A	N/A
Window allowance (days)			V1+3 (±1)	V1+7 (±1)	V1+21 (+3)	V4+3 (±1)	V4+7 (±1)	V4+21 (±3)	V1+141 (±7)	V1+386 (±7)	N/A	N/A
Venous blood sample collection for clinical safety laboratory tests ⁿ	Х			X°	X ^{e,o}		Xº					X ^d
Venous blood sample collection for antibody assays		Xe			Xe			Х	Х			
Cellular immunology (subset only)		Xe			Xe			Х	Х			
Randomization		X ^e										
Vaccination		Х			Xp							
Monitor subject for 30 minutes following vaccination ^q		Х			Х							
Examine vaccination site ^r		X ^s		Х	X ^s		Х				Xď	Xt
AE/MAAE/PIMMC/SAE assessment ^u		Х	Х	Х	Х	Х	Х	Х	X	Х	Х	Х

Table 12–1Schedule of Events, Groups A to D, G to J

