Abbreviations: AE, adverse event; ALT, alanine aminotransferase; AST, aspartate aminotransferase; DC, diary card; eCRF, electronic case report form; EOS, end of study; ET, early termination; FDA, Food and Drug Administration; MAAE, medically attended adverse event; N/A, not applicable; PIMMC, potentially immune-mediated medical condition; SAE, serious adverse event; SUSAR, suspected unexpected serious adverse reaction; ULN, upper limit of normal; Unsch, unscheduled; V, visit; WOCBP, women of childbearing potential.

^a Telephone call assessment.

^b Prior to the completion of any study-related procedures.

Protocol: BP-I-16-005 Version 2.0

H5 Influenza Vaccine With Either AS03 or MF59

- 26 February 2018
- ^c Vital sign measurements include oral temperature, pulse rate, and blood pressure. Vital signs will be measured before blood is collected, at both pre-vaccination and 30±5-minute postvaccination time points on a vaccination day. Diastolic and systolic blood pressure will be measured after the subject is seated for at least 5 minutes.
- ^d If clinically indicated.
- e Prior to vaccination.
- ^f Ask subject a standard nonleading question to elicit any medically related changes in their well-being. Ask if they have been hospitalized, had any accidents, used any new medications, received any vaccinations, or changed concomitant medication regimens (both prescription and over-the-counter medications).
- ^g Diary Card I (Days 1-8) and III (Days 22-29) will be used to collect unsolicited and solicited local and systemic reactions. Diary Card II (Days 9-21) and IV (Days 30-43) will be used to collect unsolicited AEs.
- ^h If applicable, according to the protocol period, collect and review DC with subject.
- ⁱ Use of all concomitant medications that the subject is taking at the time of Visit 1, medications taken up to 14 days prior to Visit 1, and vaccines received 12 months prior to Visit 1 will be recorded in the subject's eCRF.
- ^j Obtained by interview and by review of diary card completed by the subject.
- ^k Any physical examination findings will be collected in the eCRF for medical history data presentation.
- ¹ Targeted physical examination will be performed at the discretion of the investigator, if necessary, to evaluate AEs or clinical laboratory abnormalities. Any findings from this examination will be collected in the eCRF for AEs.

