3.3 Study Groups

This is a double-blinded study with 12 study groups (i.e. treatment groups). The summary will be based on each of the 2 adjuvants (summary table includes 6 treatment arms in one page for each adjuvant). For subjects missed the second and/or third vaccinations, the randomized treatment groups will be used for summarizing these subjects. For a complete list of study groups and corresponding vaccination and adjuvants schemes refer to Table 3-1.

4 General Statistical Considerations

For continuous variables, descriptive statistics will typically include the number of subjects, mean, standard deviation (SD), 25th percentile (Q1), median, 75th percentile (Q3), minimum, and maximum. For categorical variables, descriptive statistics will typically include the number and percentage of subjects in each category. Unless otherwise noted, data from all sites will be combined in the computation of these descriptive statistics.

In statistical summaries, mean, median, Q1, and Q3 will be displayed to one more decimal place than the original value; minimum and maximum will keep the same number of decimal places as the original value; standard deviation will be displayed to two more decimal places than the original value; percentages will generally be reported to one decimal place.

Computation for all the results will be performed using SAS[®] version 9.3 or higher computer software package.

Baseline

Unless otherwise specified, baseline will be defined as the last non-missing measurement prior to the first vaccination.

Study Day

Study Day will be calculated as event/assessment date - first dose date of IP if the assessment occurs before the first dose; Study Day will be calculated as event/assessment date - first dose date of IP + 1 Day if the assessment occurs on or after the first dose.

Subject Counts in Table Headers

The subject counts (N's) for each study group in the table header will equal the number of subjects who receive the actual treatment as the study group displayed unless otherwise specified. All other subjects who receive any vaccination different from group A-L regimen will be included in the listings and overall column (per adjuvant) if available. Overall column will be included in the tables based on randomized treatment only.

Safety Data Reporting Periods

The safety data reporting periods are shown in Table 4-1.

of Event	Collection Period: Study Days
ited AEs	Days 1-8 Post each vaccination

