9.4 Vital Sign Measurements

Vital signs to be obtained include the following:

- Blood pressure (systolic and diastolic [mm/Hg])
- Pulse rate (beats per minute)
- Oral temperature (°F)

Vital signs results will be classified according to the FDA Toxicity Grading Scale (See Appendix 3, Section 14.3, Grade 1 = Mild, Grade 2 = Moderate, Grade 3 = Severe, Grade 4 = Potentially Life Threatening) based on quantifiable criteria; vital signs results that are normal will be classified as Grade 0. This categorical data will be summarized in shift tables comparing by visit and by maximum post-baseline value with those at the baseline visit.

Summary tables presenting observed values and changes from baseline will be displayed for vital sign data by study group for subjects in the Safety Set.

All vital sign data by subject will be presented in a listing. Subjects with any clinically significant vital sign measurements will also be listed.

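### The maximum post-baseline shift covers 3 lab draws in 2-dose groups and 5 in 3-dose groups (6 vs 11 vital-sign readings), and no shift for dose 2 or 3 uses a pre-dose reference

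*SAP*

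**What the plan says.** SAP Section 4, under Baseline, sets one reference for all such summaries unless stated otherwise: "baseline will be defined as the last non-missing measurement prior to the first vaccination". Sections 9.3 and 9.4 state no other. Section 9.3 plans two shift displays for graded laboratory results: "This categorical data will be summarized in shift tables comparing by visit and by maximum postbaseline value with those at the baseline visit". Section 9.4 repeats this for vital signs: "shift tables comparing by visit and by maximum post-baseline value with those at the baseline visit". Both sections add observed values and changes from baseline by study group.

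SAP Section 3.3 puts the six arms of one adjuvant on a page. Four of these are 2-dose arms and two are 3-dose arms.

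Protocol Section 7.7.4.1 adds, for laboratory data: "Clinical safety laboratory abnormalities will be summarized at prevaccination and 7 days after each vaccination by study group". SAP Section 3.2.2.1 lists laboratory and vital-sign abnormalities among the secondary safety endpoints.

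**The concern.** A maximum rises with the number of values it is taken over. The 3-dose groups are followed for longer and read more often, and the SAP does not limit the maximum to a period that all groups share. A reader of the page sees more subjects with a worst-case abnormality in the 3-dose arms and cannot tell a dose-3 effect from the extra readings.

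The reference for later doses is a second, smaller matter. Labs are not scheduled at Visit 1, so the lab baseline is the screening draw, Day -14 to Day -3. The Day 149 draw, 7 days after dose 3, is therefore compared with a value 151 to 162 days older (148 + 3 to 148 + 14), although there is also a draw at the Day 142 visit. The 30-minute vital signs after dose 3 are compared with a reading 141 days older, although a pre-dose reading is taken the same day. Background change over those months is mixed into the shift shown after the dose.

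**Working it through.** **Nearest figure in the plan.** The documents give no figure for these tables. The closest is SAP Table 4-2 (Protocol Table 7-1), which uses the same at-least-one formula, 1 − (1 − p)^n. At p = 5% it gives 1 − 0.95^60 = 95.4% and 1 − 0.95^120 = 99.8%, as printed. All 14 cells agree to rounding.

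**Number of readings.** These are counted from Protocol Tables 12-1 and 12-2. Footnote c has vital signs measured "at both pre-vaccination and 30±5-minute postvaccination time points on a vaccination day", so each vaccination visit gives two readings.

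| | 2-dose groups (A-D, G-J) | 3-dose groups (E, F, K, L) |
|---|---|---|
| Lab draws after baseline | V3, V4, V6 = 3 | V3, V4, V6, V8, V10 = 5 |
| Vital-sign readings after baseline | V1 post, V3, V4 pre, V4 post, V6, V7 = 6 | the same 6 plus V8 pre, V8 post, V10, V11, V12 = 11 |

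Unscheduled, repeat and early-termination readings are left out.

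**Chance that the maximum is abnormal.** Let p be the probability of an abnormal reading, the same at every reading and in every group. With m independent readings the chance is 1 − (1 − p)^m. The documents give no p, so a range of 1% to 20% is assumed.

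| p | Labs, m = 3 vs 5 | Ratio | Vital signs, m = 6 vs 11 | Ratio |
|---|---|---|---|---|
| 1% | 3.0% vs 4.9% | 1.65 | 5.9% vs 10.5% | 1.79 |
| 2% | 5.9% vs 9.6% | 1.63 | 11.4% vs 19.9% | 1.75 |
| 5% | 14.3% vs 22.6% | 1.59 | 26.5% vs 43.1% | 1.63 |
| 10% | 27.1% vs 41.0% | 1.51 | 46.9% vs 68.6% | 1.46 |
| 20% | 48.8% vs 67.2% | 1.38 | 73.8% vs 91.4% | 1.24 |

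For example, at 5% the lab figures are 1 − 0.95^3 = 14.3% and 1 − 0.95^5 = 22.6%. In groups of 60 that is 8.6 vs 13.6 subjects.

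**Correlated readings.** Readings in one person are unlikely to be independent. The table below uses an equicorrelated normal threshold model with p = 5% and 1,000,000 simulated subjects.

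| Correlation | Labs | Ratio | Vital signs | Ratio |
|---|---|---|---|---|
| 0.3 | 13.01% vs 19.34% | 1.49 | 22.01% vs 32.51% | 1.48 |
| 0.5 | 11.85% vs 16.64% | 1.40 | 18.62% vs 25.87% | 1.39 |
| 0.7 | 10.28% vs 13.51% | 1.31 | 14.77% vs 19.26% | 1.30 |
| 0.9 | 7.96% vs 9.45% | 1.19 | 9.99% vs 11.85% | 1.19 |

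The formula counts any abnormal reading. A shift table also sorts subjects by baseline grade, so an abnormality already present at baseline and unchanged stays on the diagonal. The figures show the size of the artefact and do not predict the cells of the table.

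**With a common window.** If the maximum stops at V6 for labs and V7 for vital signs, the counts are 3 vs 3 and 6 vs 6 and the ratio is 1.00. At 5% with independent readings, both kinds of group then expect 14.3% and 26.5%.

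**Timing of the draws.** Table 12-1 marks the V4 safety-lab draw as taken before vaccination. In Table 12-2 the V4 and V8 safety-lab cells carry no such mark. For Groups E, F, K and L, the tables therefore do not confirm that a pre-dose lab value exists at those visits.

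**The case against.** A reader might infer that no laboratory or vital-sign change can be tied to its dose. The documents do not support that. The sentence that plans the maximum also plans by-visit shifts, and V3, V6 and V10 each fall 7 days after one dose. The dose-1 shift already has its proper pre-dose reference. Protocol Section 7.7.4.1 plans lab abnormalities before and 7 days after each vaccination. Under Protocol Section 6.2.5.3, clinically significant Grade 1 to 3 findings, ALT or AST elevations of Grade 2 or more, and all Grade 4 findings become adverse events, and SAP Section 9.1 tabulates adverse events by dose.

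A reader might also infer that the pre-dose-1 baseline is wrong. It is a legitimate choice. It shows cumulative change over the regimen, and a Day 22 reference could hide a lasting effect of dose 1. Protocol Sections 4.3 and 6.2.5.8 likewise refer ALT and AST back to the screening value.

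Nor do the 3-dose groups look worse throughout. By-visit shifts at V3, V4 and V6 compare like with like, and the same regimen under the two adjuvants has equal numbers of readings even in the maximum table. SAP Section 1 plans no formal comparison between groups for primary or secondary objectives.

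All of this stands and limits the point. It does not answer the two gaps that remain: the maximum has no common window, and no within-subject shift from the pre-dose-2 or pre-dose-3 value is specified.

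**Conclusion.** The point holds for the maximum post-baseline table, where 3-dose groups are read 5 times against 3 for labs and 11 against 6 for vital signs. At equal risk per reading this alone raises the proportion with an abnormal maximum. At an assumed 5% per reading the ratio is about 1.6 with independent readings, about 1.4 at correlation 0.5 and 1.19 at 0.9. The per-reading risk and the correlation are assumptions; the counts come from the schedules. For doses 2 and 3, the by-visit tables attach a change to the dose but measure it only from before dose 1. The consequence is for descriptive reading of secondary safety endpoints; no test is affected. This is an inexpensive improvement to the displays and does not call for replacing the planned baseline.

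**What to change.** In SAP Sections 9.3 and 9.4:

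- Show the maximum post-baseline shift for all 12 groups over the common period: V3, V4 and V6 for labs, and V1 post-dose to V7 for vital signs. Show the dose-3 period separately for Groups E, F, K and L.
- Keep the present baseline and the by-visit tables.
- Add lab shifts from V4 to V6 (all groups) and from V8 to V10 (E, F, K, L), and vital-sign shifts from the same-day pre-dose reading to the 30-minute reading for each dose.
- Confirm whether the V4 and V8 safety labs in Table 12-2 are drawn before vaccination, and reconcile that table with Table 12-1. The added lab shifts for E, F, K and L depend on it.

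The cost is revised SAP wording, a re-cut of the shift programs and a few more tables. No additional data are needed.
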